6.3 Interim Analyses, Final Analyses, and Unblinding

No formal interim analysis is planned for this study. Enrollment of subjects into the study will be paused if mortality in the treatment arm is $\geq 7\%$ higher compared to the placebo arm until the Data Safety Monitoring Board (DSMB) makes an assessment about causality, and may resume once the DSMB deems it acceptable to continue (if applicable).

The final analysis will occur after the database has been locked and the data are unblinded.

Unblinded site-specific raw data will be shared with each participating clinical site within 3 months after the clinical study report is finalized.

6.4 Pooling of Sites

Data will be pooled and analyzed across sites. Each site will follow the same protocol, will receive the same training, and will have consistent monitoring and data collection.

6.5 Treatment Compliance and Extent of Exposure

Subjects will be instructed to take a loading dose of 10 capsules (300 mcg) of study drug per day on Days 1, 2 and 3 at bedtime by the oral route. On Days 4-27, subjects will take a maintenance dose of 2 capsules (60 mcg) per day at bedtime unless otherwise directed. Extent of exposure will be assessed as the total dosage of Rayaldee (CTAP101 Capsules) received.

Study treatment compliance during the treatment period will be assessed via a patient diary and in person at all specified visits. Treatment compliance (%) will be calculated as the number of capsules that should have been taken versus the actual number taken, as evidenced by dosing records. Overall dosing compliance is defined as taking between 80% and 120% of the scheduled doses for the period of time that the subject participates in the study. Treatment compliance and extent of exposure will be listed by subject and summarized by treatment group.

6.6 Subject Disposition

Subject disposition will be tabulated and descriptively summarized for all randomized subjects by treatment group and overall. The primary reason for premature study discontinuation will be detailed together with the number and proportions of subjects discontinuing for each reason.

6.7 Demographic and Baseline Characteristics

For each analysis population, baseline subject characteristics including age, sex, race, ethnicity, height, weight, body mass index (BMI) and eGFR will be summarized by study arm (CTAP101 Capsules and placebo). Age (years) will be calculated as (date of ICF - date of birth + 1)/365, or as reported age (to the nearest month) at study entry if date of birth is not collected.

6.8 Prior and Concomitant Medications

Prior medications are defined as any continuing or new medication used within 12 weeks and discontinued before initiation of treatment on Day 1. Concomitant medications are defined as any continuing or new medication taken after treatment initiation on Day 1 or anytime thereafter until the end of the study. World Health Organization Drug Dictionary (WHODrug) Enhanced version September 2017, Format C, or later will be used to code concomitant and prior medications. Prior and concomitant medications will be tabulated by treatment group. All medications recorded on the eCRF, including start and stop (or ongoing as of) dates, AE number (if applicable), indication, dose, unit, route, and frequency will be listed.

6.9 Safety Analyses

All subjects in the Safety population will be included in the safety analysis. Statistical summary analysis of safety data will be descriptive and performed by treatment group. No inferential hypothesis testing will be performed on the safety variables with the exception of comparisons of serum calcium and serum phosphorus between treatment groups.

6.9.1 Adverse Events

All AEs will be collected on the eCRF and coded via system organ class (SOC) and preferred term using MedDRA version 23.0 or higher. Additionally, the intensity of all AEs will be coded using CTCAE v. 5.0. Detailed information collected for each TEAE will include: AE number, a description of the event, start date, end date or ongoing as of date, outcome, therapy for event, whether the AE is serious, seriousness criteria (life-threatening, death, hospitalization/prolongation of hospitalization, congenital anomaly, persistent or significant disability/incapacity, required intervention to prevent permanent impairment/ damage), severity, and relationship to the study drug. The incidence of the AEs will be summarized by treatment group for all TEAEs, potentially drug-related TEAEs, serious TEAEs, discontinuation due to TEAEs, TEAEs by relationship to study drug (definite, probable, possible, unrelated) and TEAEs by severity (mild, moderate, severe). The number and percentages of subjects with a TEAE will be summarized by SOC and preferred term and presented overall and by treatment group. TEAEs will be sorted in descending order of total incidence of SOC and preferred term within each SOC. The percentages will be based on the number of Safety subjects in a particular treatment group. If a subject has more than one TEAE that code to the same preferred term, the subject will be counted only once for that preferred term. Similarly, if a subject has more than one TEAE within a SOC category, the subject will be counted only once in that SOC category. All AEs collected on the eCRF will be included in the listings. An additional listing of all subject deaths will also be provided.

Diagnostic procedures will be collected separately in the eCRF and coded via SOC and preferred term using MedDRA version 23.0 or higher in a manner similar to AEs.

6.9.2 Physical Examinations

A brief physical examination will be performed at the screening (Visit 1) and at Visit 5/ET. Any results that are clinically significant will be reported on the MH/AE page of the CRF as appropriate. The number and percentage of subjects with transitions from normal at Screening to

clinically significant at Visit 5/ET will be presented by treatment group. A listing of physical examination data for all subjects will also be provided.

6.9.3 Vital Signs

Height, weight and BMI determinations will be recorded at Screening (Visit 1) and body weight and BMI (using screening height) at the end of the treatment period (Visit 5/ET). Observed vital sign values will be summarized descriptively by treatment group at Screening (Visit 1) and at each post-screening assessment. Changes from screening will also be included in this summarization. Summaries will include n (%), mean, SD, median, minimum, and maximum. A listing of all vital sign values will be presented by subject.

6.9.4 Electrocardiograms

Electrocardiograms (ECGs) will be performed at Screening (Visit 1), Visit 3 and Visit 5/ET. The number and proportion of subjects with overall assessments of Normal and Abnormal, as well as those assessments judged to be clinically significant will be tabulated at each visit by treatment group. Shifts in overall assessment (No Change, Normal to Abnormal, and Abnormal to Normal) from screening to each post-screening visit will also be tabulated along with a determination of clinical significance.

Other quantitative ECG parameter results will be summarized descriptively by treatment group at screening and at any subsequent visits (Visits 3 and/or 5). Changes from screening will also be included in this summarization. Summaries will include n (%), mean, SD, median, minimum, and maximum. A listing of all ECG results will be presented by subject.

6.9.5 Safety Laboratory Parameters

Descriptive statistics for clinical laboratory values and changes from baseline at each assessment time point will be presented by treatment group for each clinical laboratory parameter. Special attention will be given to changes in serum total calcium (corrected for serum albumin), serum phosphorus, and eGFR.

Secondary safety endpoints will include incidence of hypercalcemia and drug-related hyperphosphatemia. The number (n, %) of subjects with hypercalcemia (serum calcium >10.5 mg/dL) or hyperphosphatemia (serum phosphorus> 4.5 mg/dL) will be compared between study arms using a Chi-square test statistic (alpha=0.05).

A listing of all laboratory results will be presented by subject.

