9.9.3 Secondary Safety Analyses

Secondary safety endpoints for will include incidence of hypercalcemia and drug-related hyperphosphatemia. The number (n, %) of subjects with hypercalcemia (serum calcium >10.5 mg/dL) or hyperphosphatemia (> 4.5 mg/dL) will be compared between study arms using a Chi-square test statistic (alpha=0.05).

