Patients randomized to RAYALDEE experienced a greater mean (SE) increase in serum calcium (P<0.001) than patients randomized to placebo [i.e., 0.2 (0.02) mg/dL on RAYALDEE versus 0.1 (0.03) mg/dL on placebo from baseline to trial end]. Six subjects (2%) in the RAYALDEE treatment group and no subjects (0%) in the placebo group required dose reductions for protocol-defined hypercalcemia (two consecutive serum calcium values greater than 10.3 mg/dL). A total of 4.2% of RAYALDEE treated subjects and 2.1% of placebo treated subjects experienced at least one elevation in serum calcium above the upper limit of normal (10.5 mg/dL).

Increase in Serum Phosphorus

Patients randomized to RAYALDEE experienced a greater mean (SE) increase in serum phosphorus than patients randomized to placebo [i.e., 0.2 (0.03) mg/dL on RAYALDEE versus 0.1 (0.04) mg/dL on placebo from baseline to trial end]. One subject (0.4%) in the RAYALDEE treatment group met protocol-defined hyperphosphatemia (two consecutive serum phosphorus values greater than 5.5 mg/dL deemed to be study drug related) compared to no subjects in the placebo group. A total of 45% of RAYALDEE treated subjects and 44% of placebo treated subjects experienced at least one elevation in serum phosphorus above the upper limit of normal (4.5 mg/dL).

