14.3.1.4	Incidence of Treatment-Emergent Adverse Events Leading to Discontinuation of Study by System Organ Class and Preferred Term: Safety Population
14.3.1.5	Incidence of Treatment-Emergent Adverse Events Leading to Discontinuation of Treatment by System Organ Class and Preferred Term: Safety Population
14.3.1.6	Incidence of Treatment-Emergent Adverse Events Definitely Related to Study Drug by SOC and Preferred Term: Safety Population
14.3.1.7	Incidence of Treatment-Emergent Adverse Events Probably Related to Study Drug by SOC and Preferred Term: Safety Population
14.3.1.8	Incidence of Treatment-Emergent Adverse Events Possibly Related to Study Drug by SOC and Preferred Term: Safety Population
14.3.1.9	Incidence of Treatment-Emergent Adverse Events Unrelated to Study Drug by SOC and Preferred Term: Safety Population
14.3.1.10	Incidence of Mild Treatment-Emergent Adverse Events by SOC and Preferred Term: Safety Population
14.3.1.11	Incidence of Moderate Treatment-Emergent Adverse Events by SOC and Preferred Term: Safety Population
14.3.1.12	Incidence of Severe Treatment-Emergent Adverse Events by SOC and Preferred Term: Safety Population
14.4.1	Subjects with Physical Examination Shift from Normal at Screening to Clinically Significant at End of Trial: Safety Population
14.4.2	Vital Sign Results and Change from Baseline to Each Visit: Safety Population
14.4.3.1	ECG Interpretation and Shifts from Screening to Each Visit: Safety Population
14.4.3.2	ECG Results at Each Visit and Change from Baseline: Safety Population
14.4.4.1	Hematology Results at Each Visit and Change from Baseline: Safety Population
14.4.4.2	Serum Chemistry Results at Each Visit and Change from Baseline: Safety Population
14.4.4.3	Incidence of Hypercalcemia and Hyperphosphatemia Overall and at Each Visit: Safety Population

TREATMENT COMPLIANCE

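### The endpoint named drug-related hyperphosphatemia is tested as a count of any phosphorus above 4.5 mg/dL, with no relatedness rule and no baseline rule

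*SAP*

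**What the plan says.** - **Name.** SAP 6.9.5: "Secondary safety endpoints will include incidence of hypercalcemia and drug-related hyperphosphatemia". Protocol 9.9.3 says the same: "Secondary safety endpoints for will include incidence of hypercalcemia and drug-related hyperphosphatemia".
- **Count.** The next sentence of SAP 6.9.5 takes the number of subjects with hypercalcemia (above 10.5 mg/dL) or "hyperphosphatemia (serum phosphorus> 4.5 mg/dL) will be compared between study arms using a Chi-square test statistic (alpha=0.05"). Protocol 9.9.3 matches: "hyperphosphatemia (> 4.5 mg/dL) will be compared between study arms using a Chi-square test statistic (alpha=0.05").
- **Output.** SAP 8.1, Table 14.4.4.3, is titled "Incidence of Hypercalcemia and Hyperphosphatemia Overall and at Each Visit". It carries neither a drug-related nor a treatment-emergent qualifier.
- **Status of the test.** SAP 6.9 and protocol 9.9 allow inferential testing of safety variables only for serum calcium and serum phosphorus.
- **Relatedness.** Protocol 6.7.5 has the investigator rate relationship for adverse events. Under 6.7.6 a laboratory change is an adverse event only if clinically significant. Abnormal values are presumed so unless the investigator marks them otherwise.
- **Entry.** Protocol 4.3 excludes a history of hyperphosphatemia but sets no screening phosphorus limit. For calcium it excludes 9.8 mg/dL or more in the last three months.
- **Earlier trials.** The package insert (protocol Appendix 2, insert section 6.1) reports: "A total of 45% of RAYALDEE treated subjects and 44% of placebo treated subjects experienced at least one elevation in serum phosphorus" above 4.5 mg/dL. It separately reports a stricter definition: "two consecutive serum phosphorus values greater than 5.5 mg/dL deemed to be study drug related".

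**The concern.** There are two gaps.

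First, the name promises a judgement that the drug caused the elevation, and the counting rule contains none. A result from this test could not properly be reported under the endpoint's name.

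Second, the rule does not say whether a subject already above 4.5 mg/dL before the first dose can be an event. If such subjects are counted, they add events to both arms that the drug cannot have caused, and a real difference is harder to see.

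Phosphorus is one of only two laboratory variables given a formal safety comparison, so a non-significant p-value is likely to be read as reassurance. The reader should know what was counted.

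**Working it through.** **1. Name against count**

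| Feature | Endpoint as named | Count as tested | Insert's stricter definition |
|---|---|---|---|
| Cut-off | not given | above 4.5 mg/dL | above 5.5 mg/dL |
| Confirmation | not given | none | two consecutive values |
| Relatedness | required by the name | none | required |
| Baseline rule | not given (incidence may imply new) | none stated | none stated |

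The counting sentence does not refer to adverse-event ratings. A value just above 4.5 mg/dL that the investigator marks as not clinically significant receives no rating at all. The stated count therefore cannot yield the named endpoint.

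**2. The package insert's figures**

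Denominators are 285 active and 144 placebo.

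- Counts that round to the reported percentages: 127 to 129 of 285 (45%) and 63 or 64 of 144 (44%).
- Taking 128 and 64: 128/285 = 0.449, 64/144 = 0.444, pooled 192/429 = 0.448. The standard error is √[0.448 × 0.552 × (1/285 + 1/144)] = 0.051, so z = 0.0047/0.051 = 0.09 and p = 0.93. Over all possible counts, p runs from 0.77 to 0.98.
- Under the stricter definition, 1/285 = 0.35%, reported as 0.4%, against none on placebo.

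An any-value count and a drug-related count gave very different numbers in the same trials. The insert does not split the 45% and 44% into elevations present at baseline and new ones.

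**3. Baseline handling elsewhere**

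SAP 6.1 defines baseline as the most recent pre-dose result. SAP 6.9.2 and 6.9.4 use changes from the screening assessment for physical examinations and ECGs. Protocol 6.7.8 defines treatment-emergent adverse events. None of these rules is extended to the phosphorus count. Chemistry is drawn at screening (protocol 7.1.1), so a baseline value exists.

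**4. Direction of the effect if baseline elevations are counted**

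Let b be the share elevated at baseline, p the new-elevation rate among the rest in each arm, d the difference in p between arms, and n the number per arm. Assume that every baseline-elevated subject counts as an event.

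- Any-value rate in an arm: b + (1 − b)p. Difference between arms: (1 − b)d.
- (Difference/SE)², any-value: n(1 − b)d² / Σ(1 − p)[p + b(1 − p)].
- (Difference/SE)², new elevations only, with n(1 − b) per arm: n(1 − b)d² / Σp(1 − p).

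Sums run over the two arms. The first denominator is larger whenever b > 0, so the any-value count is less sensitive even after the smaller sample is allowed for.

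Illustration, all inputs assumed: n = 80, b = 10%, p = 5% on placebo and 15% on active.

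- Any-value: rates 14.5% and 23.5%, difference 9 points, SE √[(0.145 × 0.855 + 0.235 × 0.765)/80] = 6.2 points, ratio 1.46.
- New only, 72 per arm: difference 10 points, SE √[(0.05 × 0.95 + 0.15 × 0.85)/72] = 4.9 points, ratio 2.03.

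This shows direction only; b and p are unknown here. The loss is smaller if some baseline-elevated subjects normalise and the screening value is not counted.

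**The case against.** The strongest reply has four parts.

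- **Validity.** In a blinded randomised comparison, the difference between arms is itself the evidence on drug attribution, and baseline elevations balance in expectation. This stands. A reader might infer that the test is invalid; it is not. The defects are the label and a possible loss of sensitivity.
- **Silence.** The word incidence ordinarily means new events, and SAP 6.1 separates pre-dose from post-dose values. A reader might infer that baseline-elevated subjects are counted as events. The documents do not say so. They also do not say the opposite, and nothing turns the word into a counting rule.
- **Other outputs.** Adverse events are tabulated by relationship (Tables 14.3.1.6 to 14.3.1.9), phosphorus change from baseline is summarised by arm, and all values are listed. This stands: a signal would not rest on one chi-square. These outputs do not reconcile the endpoint's name with its test.
- **The 45% against 44%.** A reader might take 44% as this trial's background and conclude that the test has almost no power. The documents do not support that. The figure comes from stage 3 or 4 kidney disease with secondary hyperparathyroidism and up to 6 months of dosing. Here dosing lasts 27 days in patients with mild to moderate COVID-19, although stage 3 or 4 patients may enrol. If most of the 44% were new elevations, a baseline rule would leave that background in place. Power at assumed backgrounds, with 80 per arm held fixed, compares assumptions and does not measure what the edit gains.

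**Conclusion.** The mismatch between name and count is certain from the text of both documents and depends on no assumption. The missing baseline rule is an omission. Its consequence is conditional: if baseline elevations count, sensitivity falls, by an amount the documents do not allow anyone to compute. The insert's figures support one inference only, that an any-value count at 4.5 mg/dL can be non-specific.

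This is a minor point. It touches neither the efficacy conclusions nor the validity of the comparison, but it affects how one of two formal safety tests is named and read.

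**What to change.** In SAP 6.9.5, with protocol 9.9.3 and the title of Table 14.4.4.3 aligned:

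1. Call the endpoint hyperphosphatemia and keep the stated 4.5 mg/dL cut-off.
2. For the chi-square test, count subjects at or below 4.5 mg/dL at baseline who have any value above 4.5 mg/dL after the first dose. The denominator is subjects at or below 4.5 mg/dL at baseline.
3. State the parallel rule for calcium at 10.5 mg/dL. It will matter little given the calcium entry limit.
4. Show subjects elevated at baseline in a descriptive shift table, so that worsening among them is visible.
5. For drug-related hyperphosphatemia, refer to the planned adverse-event tables by relationship. Align their categories first: protocol Table 3 grades events as not related, unlikely related, possibly related or related, while SAP 6.9.1 and Tables 14.3.1.6 to 14.3.1.9 use definite, probable, possible and unrelated.

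The cost is a few sentences and one descriptive table, from data already collected. The tested denominator becomes 80(1 − b) per arm: 76 if 5% are elevated at baseline, 72 if 10%. SAP section 1 lets the SAP prevail over the protocol on analyses, so the SAP edit alone would govern. It should be made before unblinding.

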4.3 Exclusion Criteria

Subjects who meet any of the following criteria will be excluded from the study:

- Clinical signs indicative of severe or critical COVID-19 severity (eg, oxygen saturation < 94% on room air or respiration rate > 30 bpm);
- 2) Pregnant or lactating women who are breastfeeding;
- 3) Use of systemic glucocorticoid medications in the last six months;
- 4) Recent history (previous 12 months) of primary hyperparathyroidism, kidney stones, hypercalciuria and/or hypercalcemia;
- 5) History of a chronic granuloma-forming disease (eg, sarcoidosis);
- 6) History of tuberculosis or histoplasmosis;
- 7) History of chronic liver disease;

- 8) History of (previous 12 months) of cardiac event indicative of chronic cardiovascular diseases including congestive heart failure, poorly controlled hypertension and arrhythmias;
- 9) History in the past five years of multiple myeloma or carcinoma of the breast, lung or prostate;
- Any surgical or medical condition which might significantly alter the absorption, distribution, metabolism, or excretion of vitD or 25D (eg, small bowel resection, history of Crohn's disease or ulcerative colitis);
- 11) Ongoing treatment with thiazide diuretics;
- 12) History of hyperphosphatemia, hyperuricemia and gout;
- 13) Renal impairment measured as eGFR< 15 mL/min/1.73m² on serum creatinine in the last three months;
- 14) Serum calcium $\geq 9.8 \text{ mg/dL}$ in the last three months;
- 15) Evidence of existing or impending dehydration;
- 16) Known or suspected to have hypersensitivity to any of the constituents of the study drug; and/or,
- 17) Currently participating in, or have participated in, an interventional/investigational study within 30 days prior to study screening.

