3 STUDY DESIGN

3.1 Overview

This is a phase 2 multi-center, randomized, double-blind placebo-controlled study to evaluate the safety and efficacy of Rayaldee (CTAP101 Capsules) to treat adult subjects with unresolved symptoms of mild to moderate COVID-19 who test positive for SARS-CoV-2 via any FDA-approved diagnostic test. Subjects will be randomized to receive either oral Rayaldee (CTAP101 Capsules) or matching placebo. Approximately 80 subjects will be randomized in a blinded manner to each of the Rayaldee (CTAP101 Capsules) and placebo treatment groups, for a total of approximately 160 subjects.

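### The only named between-arm test for calcium and phosphorus counts subjects above a limit, which is insensitive to a small shift; the plan specifies no between-arm estimate of change with a confidence interval.

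*SAP*

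**What the plan says.** SAP 6.9 makes safety analysis descriptive and rules out inferential testing "with the exception of comparisons of serum calcium and serum phosphorus between treatment groups". That sentence names no method, model or time point.

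The method comes in SAP 6.9.5 and, in the same terms, Protocol 9.9.3. The secondary safety endpoint is the number of subjects with "hypercalcemia (serum calcium >10.5 mg/dL") or phosphorus above 4.5 mg/dL, and these numbers "will be compared between study arms using a Chi-square test statistic (alpha=0.05").

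SAP 6.9.5 also promises special attention to changes in corrected calcium, phosphorus and eGFR. For these it specifies descriptive statistics by arm at each time point (Table 14.4.4.2). Neither document specifies a between-arm difference or a confidence interval for change. Protocol 6.4.1 schedules blood draws at Screening and on Days 7, 14, 21 and 28.

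**The concern.** Calcium and phosphorus are the two safety variables that the plan singles out for formal comparison, yet the comparison uses only whether a subject crossed a limit. Exclusion 14 in Protocol 4.3 removes subjects whose calcium was 9.8 mg/dL or more "in the last three months". A subject just below that level must therefore rise by more than 10.5 - 9.8 = 0.7 mg/dL to be counted. The package insert in Protocol Appendix 2 (section 6.1) reports mean changes of "0.2 (0.02) mg/dL on RAYALDEE versus 0.1 (0.03) mg/dL on placebo from baseline to trial end". A shift of that size moves few subjects over the line.

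At stake is how the result can be interpreted. The one formal calcium comparison could be non-significant when calcium had moved modestly, with no planned interval beside it to show which differences remain compatible with the data. The three 300 mcg loading doses lie outside the 30 or 60 mcg daily dosing behind the insert's figures, so the size of any shift here is not known in advance.

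**Working it through.** The documents state no power for this comparison, so there is no figure to reproduce.

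**Inputs**
- Per arm, n = 80. SAP 3.1: "Approximately 80 subjects will be randomized in a blinded manner to each of" the two groups.
- Calcium above 10.5 mg/dL at least once: 4.2% active, 2.1% placebo (Protocol 1.5; insert 6.1).
- Phosphorus above 4.5 mg/dL at least once: 45% v 44% (insert 6.1).
- Mean change (SE): calcium 0.2 (0.02) v 0.1 (0.03) mg/dL; phosphorus 0.2 (0.03) v 0.1 (0.04) mg/dL, with 285 active and 144 placebo subjects (insert 6.1).
- Alpha 0.05; a 1-df Chi-square is two-sided.

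**1. Planned calcium test.** Expected counts are 80 x 0.042 = 3.4 and 80 x 0.021 = 1.7. The Pearson statistic is (difference in proportions)² / [p(1-p)(2/80)], with p the pooled proportion. It rejects at 3.841 or more. With 2 placebo subjects above the limit, 8 active give 0.075² / (0.0625 x 0.9375 x 0.025) = 3.840, just short. Nine are needed: 0.0875² / (0.06875 x 0.93125 x 0.025) = 4.78.

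Summing the probability of every rejecting table over two Binomial(80) arms, with placebo at 2.1%:

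| Active rate | Exact power |
|---|---|
| 4.2% | 10.1% |
| 8% | 38% |
| 10% | 55% |
| 12% | 71% |
| 15% | 88% |

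At 4.2% v 2.1%, the normal approximation gives 11.5%, and Fisher's test or a continuity correction 2.9%. About 1,085 per arm would be needed for 80% power.

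**2. Planned phosphorus test.** At 45% v 44%, exact power is 4.9%, in effect the alpha level.

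**3. Mean change at one visit.** SD = SE x √n.
- Calcium: 0.02 x √285 = 0.34; 0.03 x √144 = 0.36.
- Phosphorus: 0.03 x √285 = 0.51; 0.04 x √144 = 0.48.

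The SE of a between-arm difference is SD x √(2/80): 0.054-0.057 for calcium and 0.076-0.080 for phosphorus. Power is Φ(difference/SE - 1.96), the opposite tail being negligible.

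| Variable | Difference (mg/dL) | Power |
|---|---|---|
| Calcium | 0.10 | 42-46% |
| Calcium | 0.20 | 94-96% |
| Phosphorus | 0.10 | 24-26% |

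The insert's SEs are rounded. At the edges of that rounding, calcium power at 0.10 runs from 32% to 65%. The 95% CI half-width for calcium is 1.96 x 0.054 to 1.96 x 0.057, or about 0.11 mg/dL.

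**4. Using all four visits.** The average of four visits has SD 0.345 x √[(1 + 3ρ)/4], where 0.345 is the pooled SD and ρ the between-visit correlation. The documents do not give ρ. Assuming 0.3 to 0.7, calcium power at 0.10 is 76% down to 55%.

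**5. The earlier trials as illustration.** The percentages imply 12 of 285 v 3 of 144 subjects above 10.5 mg/dL (inferred counts), for which the Chi-square p is 0.26. The insert reports P<0.001 for the mean change in the same data.

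**The case against.** **The 10% is not this trial's planned power.** This stands. The 4.2% and 2.1% are background results in stage 3-4 kidney disease, over 26 weeks, at 30 or 60 mcg daily. A reader might infer that the planned test could hardly detect any calcium effect. The documents do not support that: if loading pushed 15% of active subjects over the limit against 2.1% on placebo, power would be 88%.

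**Comparing means does not rescue the small effect.** This also stands. At 0.10 mg/dL a single-visit test is more likely than not to be non-significant, and phosphorus is worse. The gain from repeated visits rests on an assumed correlation. The case for the model is the estimate and its interval rather than adequate power.

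**Calcium change is already reported.** Partly. Means and SDs by visit and arm are planned, so a reader could work out an unadjusted interval. The exception in SAP 6.9 is also broad enough to admit a comparison of means. But no such comparison is specified, and one chosen after unblinding would not be prespecified.

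**The threshold is a legitimate endpoint.** Agreed. Incidence of hypercalcemia is a declared secondary safety endpoint, and 10.5 mg/dL is also a limit used in the calcium rules of Protocol 5.3.2. Hazard detection during the trial rests on those individual rules and on the DSMB's unblinded safety monitor (Protocol 6.6), not on this test. Nothing here argues for displacing the endpoint.

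**Conclusion.** The concern holds as a gap in estimation. The only between-arm calcium and phosphorus comparison with a named method is insensitive to modest shifts: about 10% power for calcium and 5% for phosphorus if the earlier trials' crossing rates recurred at 80 per arm. With expected calcium counts near 3.4 and 1.7, the large-sample Chi-square is itself doubtful. Mean change uses the same samples and is more sensitive, but it too is not well powered at 0.10 mg/dL.

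The calcium figures rest on crossing rates and SDs carried over from a different population, duration and dosing, and on about 80 subjects per arm with data. Four post-baseline draws are scheduled, but Protocol 6.4.2 says missed samples are generally not redrawn, so some subjects will have fewer.

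Two stronger readings fail. The plan does not ignore calcium change, since it is summarised at every visit. Nor does either document say that a non-significant count would be reported as no effect; that is a risk of interpretation which an interval would reduce. No primary efficacy conclusion is affected.

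**What to change.** In SAP 6.9.5, alongside the incidence endpoint, add a repeated-measures model of change from baseline in corrected serum calcium over Days 7, 14, 21 and 28, with baseline value, arm, visit and arm-by-visit as terms. Report the between-arm difference and 95% CI at each visit, and do the same for phosphorus. State that the model is for estimation.

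Keep the counts above 10.5 and 4.5 mg/dL and report them with exact confidence intervals. Add a sentence that a non-significant threshold comparison is not to be taken as absence of a calcium effect.

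The cost is SAP wording, one model and one table, made before unblinding and using samples already scheduled. For the sponsor, the downside is that a small calcium rise is more likely to be shown.
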